## **AIMS**

### **Aim 1: Estimate ASE and ACE sensitivity and specificity.**

Hypothesis: ASE and ACE sensitivity will be  $\geq 70\%$  and  $\geq 78\%$ , respectively, at Visit 1; specificity will be  $\geq 90\%$  on both exams, and there will be no difference in ASE sensitivity between Houston and Chicago clinics.

Objective: Our objective in this aim is to compare the men's ASE or ACE result with the clinician gold-standard DARE to determine sensitivity and specificity for each exam at two time points.

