## STATISTICAL ANALYSIS

### Aim 1

The central hypothesis is that both ASE and ACE at Visit 1 will have  $\geq 70\%$  sensitivity and  $\geq 90\%$  specificity using the clinician DARE as the gold standard. We will test our central hypotheses at Visit 1 by comparing ASE and ACE sensitivity and specificity to random guessing (i.e., sensitivity and specificity=50%) using a one-sample test for proportion. We will then conduct a test of equivalence using two, one-sided likelihood score tests to compare ASE sensitivity in Houston vs Chicago clinics to determine if the ASE performance is equivalent in each city; thus, we will assess the homogeneity of Houston and Chicago sensitivity before combining results. We focus on sensitivity since this factor performed worse than specificity in the pilot study and had wide confidence limits. Sensitivity will also be stratified by other factors, for example location (anal canal vs perianal) and co-morbidities, to determine the effect on sensitivity. Tests will be two-sided with a 0.05 alpha. We will estimate percent agreement, positive predictive value, negative predictive value and perform receiver operating characteristic (ROC) curve analysis for a binary outcome.

To test our central hypothesis, our pilot data indicate 1) 11% of persons will have condyloma, hemorrhoids, skin tags, scars, or malignant tumors at Visit 1 at the anal canal or perianal region, and 2) a sensitivity of  $\geq 70\%$  on ASE and 78% on ACE and specificity  $\geq 90\%$  for both at Visit 1. Given a null value for sensitivity and specificity of 50% (since we seek to rule out accuracy due only to chance), our power to detect sensitivity  $\geq 70\%$  among 600 individuals is 0.90 and 0.81 among 200 couples. Power to detect specificity  $\geq 90\%$  among both individuals and couples is  $>0.90$ . For multiple comparisons we will use the False Discovery Rate. Using a test of equivalence, our hypothesis of no difference in ASE sensitivity between Houston and Chicago assumes that a difference of less than 0.15 constitutes equivalent sensitivity given that a smaller difference may have little practical relevance for adjusting the protocol in either city. Under this definition of equivalence, we have at least 0.87 power to detect a lack of equivalence in sensitivity between the cities if the actual observed difference ranges from 0 to 0.05. Power was assessed with PASS13.

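### Aim 1 places a Houston–Chicago equivalence test before combining ASE sensitivity, gives no rule for failure, and on the plan's own inputs the test would almost always fail even if the cities were identical

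*Combined protocol and SAP*

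**What the plan says.** Under Statistical Analysis, Aim 1, Visit 1 sensitivity and specificity are each compared with 50% "using a one-sample test for proportion". The next step is the city comparison: "We will then conduct a test of equivalence using two, one-sided likelihood score tests to compare ASE sensitivity in Houston vs Chicago clinics". The sentence then gives the reason for that step: "thus, we will assess the homogeneity of Houston and Chicago sensitivity before combining results". The general rule on significance is "Tests will be two-sided with a 0.05 alpha".

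The planning inputs are in the same section. They are "11% of persons will have condyloma, hemorrhoids, skin tags, scars, or malignant tumors at Visit 1", an assumed sensitivity of 70% or more for ASE, and power for sensitivity stated as "among 600 individuals is 0.90 and 0.81 among 200 couples". A city difference below 0.15 counts as equivalent, and power of at least 0.87 is claimed for differences from 0 to 0.05.

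The Aims section also lists the city comparison as an Aim 1 hypothesis in its own right: "there will be no difference in ASE sensitivity between Houston and Chicago clinics". The Sample Size section gives 400 participants per city over both exam types. No section says what is done with the pooled ASE result if equivalence is not shown.

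**The concern.** The wording links a formal test to the decision to combine the cities, yet gives no consequence for either outcome. The order is also unclear. The one-sample tests come first and the equivalence test follows, but the equivalence test is also meant to precede combining. The stated power for ASE is already a figure for both cities together.

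This would matter little if the test were likely to succeed. If it is nearly certain to fail, the analyst will reach the point that the plan leaves open: combine anyway, or report by city. That choice would be made with the data in view, on one of the main Aim 1 results. A failed equivalence test with few abnormal exams per city mostly reflects imprecision. It gives no ground for treating as different two clinics that, according to the Visit 1 Overview, follow identical protocols.

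**Working it through.** **Inputs.** From Statistical Analysis, Aim 1: 600 individuals doing the ASE, 11% abnormal, sensitivity 0.70, null value 0.50, two-sided alpha 0.05, margin 0.15. Assumptions: the 600 split equally by city, and each one-sided equivalence test is run at 0.05.

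**Denominators.** Sensitivity is measured only in people whose clinician exam (DARE) is abnormal.
- Both cities: 600 × 0.11 = 66.
- One city: 300 × 0.11 = 33.
- Upper case, if all 400 participants in a city did the ASE: 400 × 0.11 = 44.

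**1. The plan's pooled power.** Exact binomial test, n = 66:
- Reject at 42 or more, since P(X ≥ 42 | 0.50) = 0.018, which is below 0.025.
- Power = P(X ≥ 42 | 0.70) = 0.895.

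This reproduces the stated 0.90, so that figure belongs to the two cities combined.

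**2. The equivalence test at the planned sensitivity.** The simple 90% interval for the city difference has half-width

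1.645 × √(2 × 0.70 × 0.30 / 33) = 0.186.

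This exceeds the margin of 0.15, so under this approximation the interval cannot fit inside ±0.15, even with an observed difference of zero.

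The score test that the plan names gives the same message. Take identical results of 23/33 in both cities. The estimates constrained to differ by 0.15 are 0.612 and 0.762, so

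z = 0.15 / √[(0.612 × 0.388 + 0.762 × 0.238) / 33] = 0.15 / 0.1127 = 1.33.

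This is below the 1.645 required. With equal counts in the two cities, and sensitivity above one half, the test first succeeds at 29/33 (88%).

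**3. Probability that equivalence is shown when the cities are truly identical.** Full enumeration of both binomials, score tests at ±0.15:

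| True sensitivity, both cities | 33 per city | 44 per city |
|---|---|---|
| 0.70 | 0.0001 | 0.010 |
| 0.80 | 0.014 | 0.104 |
| 0.85 | 0.066 | 0.217 |
| 0.90 | 0.20 | 0.447 |

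With 33 per city and true sensitivities of 0.75 and 0.70, the probability is 0.0005. If each one-sided test were run at 0.025, it would be 0.0000 to four decimals at 0.70, with 33 or with 44 per city.

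**4. The plan's 0.87.** The same method gives 0.867 for 0.75 against 0.70 when 300 per city is used as the denominator. That is all ASE participants, not those with an abnormal exam. The stated figure therefore gives no assurance that the test would succeed on the people in whom sensitivity is measured.

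**5. If the cities were analysed separately.** The plan does not provide for this; it shows what hangs on the reading. Exact binomial test, n = 33, reject at 23 or more (upper tail 0.0175):
- Power in one city: 0.599.
- Both cities succeed: 0.599² = 0.36.
- Exactly one succeeds: 2 × 0.599 × 0.401 = 0.48.

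**The case against.** The strongest reply is that the plan contains no such condition. It speaks of assessing homogeneity, not of having to show it. The one-sample test comes first, with no city qualifier, and its power is stated for all 600 individuals. No section provides for a Houston-only or Chicago-only test, so the figures of 0.60, 0.36 and 0.48 describe a fallback that the plan never mentions. The city comparison also has purposes of its own: it is an Aim 1 hypothesis, the Study Purpose section wants to see whether another clinic can replicate the pilot, and the margin is justified by its relevance to adjusting the protocol in either city.

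Most of this stands. A reader might infer that the cities may be combined only after equivalence is shown, that the pooled test would otherwise be disallowed, or that separate city tests are the planned route. The documents support none of these. The reply also rightly limits the scope: no city step is attached to ACE sensitivity or to specificity. And the city hypothesis should stay in Aim 1, since demoting it in the analysis section alone would create a new inconsistency with the Aims.

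Two things remain. The plan gives assessment before combining as the purpose of the test and does not say how the result bears on combining. And the instrument chosen would almost surely return a negative result on the planned numbers, so the unanswered case is the expected one. Correcting the 0.87 alone would not say what to do when it arises.

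**Conclusion.** The point holds in a limited form. The plan puts a city equivalence test ahead of combining ASE sensitivity, leaves the consequence of failure unstated, and is ambiguous about the order of the steps. At the planned 70% sensitivity the test would succeed about once in 10,000 trials with 33 abnormal exams per city, and about once in 100 with 44, even if the cities did not differ at all. It therefore cannot inform the decision to pool.

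The plan's pooled power is sound (0.895 against 0.90). It would be lost only if someone treated the city result as a condition for pooling, which the text neither states nor rules out.

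The 33 per city rests on an equal split of ASE participants, which the documents do not give. The conclusion does not depend on the exact split. It weakens as sensitivity rises well above plan, but at 90% sensitivity with 33 per city equivalence is still missed about four times in five.

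**What to change.** In Statistical Analysis, Aim 1:
- State that Visit 1 ASE sensitivity pooled over the two cities is the primary ASE estimate and test, whatever the city comparison shows.
- Delete the words that place the homogeneity assessment before combining.
- Keep the Houston–Chicago comparison as the separate hypothesis listed under Aim 1. Report the difference with its 90% CI beside the city-specific estimates, and state that it does not decide whether the data are pooled.

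The cost is wording only. No data, visits or sample size change, and the city-specific results are still reported.

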## BACKGROUND

Anal cancer is a common cancer among gay, bisexual and other men having sex with men (MSM). Its annual incidence is approximately 50-fold and 5-fold higher among HIV-positive MSM and HIV-negative MSM, respectively, compared to the rest of the general population. Like cervical cancer, it is primarily caused by human papillomaviruses (HPV). Unlike cervical cancer, there is no efficacious treatment for anal precancers as there is for cervical precancers. To date, randomized clinical trials have failed to find an efficacious treatment although other trials continue; thus, professional societies recommend an annual Digital Anal Rectal Exam (DARE) for detection of anal abnormalities, including small tumors, among all MSM. But DARE is underutilized, e.g., most persons, regardless of HIV do not receive an annual DARE and most HIV physicians do not perform the exam. Therefore, alternative methods for early detection are needed because early detection of small tumors is associated with >85% 5-year survival.

To increase detection of anal canal tumors, our NCI-funded phase II pilot study in Houston, Texas determined it was feasible to teach MSM to palpate their own, or their companion's, anal canal. Acceptability was 94% among 148 individuals doing the exam on themselves (anal self-exam, ASE) and 92% among 52 couples doing the exam on their companion (anal companion

exam, ACE). There was 93% concordance between the clinician's gold-standard DARE and the participants' ASE or ACE for any anal canal abnormality.

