## **SAMPLE SIZE**

800 participants completing Visit 1: 400 in Chicago and 400 in Houston

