The first 40 persons in each city will receive a second DARE done by another experienced clinician immediately after the first DARE done by the primary clinician. The clinicians will be kept separate for the two DAREs and not disclose their findings to each other. The second DARE is done to assess the reliability and repeatability of the primary clinician’s DARE.

Once the clinician leaves the exam room, participants will remain and conduct the ASE/ACE. Participants will be trained to stop the procedure if pain is felt. The participant will record on a form the ASE/ACE result: either normal or abnormal. The participant will inform staff that the ASE/ACE is complete. If the participant detects an abnormality, staff will ask if the abnormality was at the perianus and/or anal canal, what it felt like, (i.e., hard or soft) and its size (using varying sizes of circles on paper). Persons will then complete a Post-Exam CASI in the exam room (one member of a couple will do the CASI in another room to give each participant privacy). The couples’ protocol mirrors the individuals’ protocol except that each partner will ask the other for consent before performing the ACE. Prostate and distal rectal palpation will neither be taught nor expected.

The Visit 1 post-exam CASI requires ~20 minutes to complete and asks about ASE/ACE acceptability and self-efficacy, in addition to intentions-to-seek subsequent care, body positioning for the exam, history of anal self-exams, alcohol use, recent sexual behavior (type and frequency), and anogenital hygiene. Questions to support cost effectiveness analysis are included.

While the participant completes the post-exam CASI, the study coordinator will use REDCap to randomize the participant (Arm 1 – practice or Arm 2 – control); if the person is a true negative (the coordinator will possess both participant and clinician results at this point) the study coordinator will check REDCap to determine if this true negative will receive a qualitative interview.

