## BURDEN OF TIME ON PARTICIPANTS DOING THE ASE

Activity	Duration
Pre-Visit 1 - Consenting.	12 min
Pre-Exam Online Survey	8 min
Visit 1	
1. Appointment greeting and photo ID check	1 min
2. Body measurements and COVID-9 symptom check	3 min
3. Anal anatomy and pathology and self-/companion exam education (Visit 1 only)	10 min
4. Anal swab	2 min
5. DARE	2 min
6. Anal-self exam or Anal companion exam	10 min
7. Post-Exam CASI	20 min
8. Results including referral or schedule for treatment if needed	7 min
	Total time
	75 min
Other: for first ~40 persons in each city, second DARE (QA and reliability study)	2 min
Other: estimated 28 persons in each city will have discordant result and clinician will offer to give participant another DARE to adjudicate	2 min
Other: for an estimated 65 persons in each city, a qualitative interview will be done	15 min

Note. Persons in couples doing the ACE at Visit 1 will require about 90 minutes for the visit. For Visit 2, persons will not receive the anal anatomy/pathology and ASE/ACE face-to-face education. Rather, they will be given instructions and asked to do the exam without benefit of a training session with study staff; then the clinician will do a DARE and provide results and any needed referrals during the same face-to face.

Activity	Duration
Immediately before Visit 2	
1. Pre-Visit 2 Pre-Exam Online Survey	10 min
2. Anal-self exam or Anal companion exam	8 min
3. COVID-19 Symptom Online Survey	3 mins
During Visit 2	
4. Appointment greeting, body measurement [weight and waist circumference] ID confirmation	3 min
5. Anal swab, DARE and results with clinician including referral or schedule for treatment if needed	5 min
6. Post-Exam CASI	20 min
	Total clinic time
Other: estimated 25 persons will have discordant result and clinician will offer to give participant another DARE to adjudicate	28 min

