For the Aim 2 hypothesis, that practice will be associated with concordance in all persons at Visit 2, sample size will be adjusted downward by dropouts and non-resolving abnormalities from Visit 1. We expect 11% of persons ( $n=88$ ) to have an abnormality at Visit 1 (based on pilot data) with most of these being hemorrhoids and condyloma. We conservatively expect 50% of hemorrhoids and condyloma to resolve in 9 months; thus, there will be a minimum of 44 non-resolving events from Visit 1 and another 10% of persons will dropout ( $800-44=756$ ;  $756-76=680$ ). We have 80% power to detect an odds ratio of at least 1.55 or larger if concordance is 85% and  $n=680$ .

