### **Informed Consent Process**

The process for obtaining informed consent will use a video conference or a phone call to a person with a smart phone. Persons who do not have access to this technology will be consented in person.

At the beginning of the electronic consent meeting (pre-arranged by appointment), staff will ask participant to confirm email address and name and then use REDCap to send the person a link by email or text (depending upon technology used by the person). Person will click on the received link to open the ICF in REDCap. Receipt of the unsigned ICF on the computer/tablet or smart phone, will be confirmed by the participant before beginning the consent session. With delivery of REDCap electronic versions of the ICF, both study staff and participant will now be viewing the study ICF. Study staff will explain study procedures, risks, benefits, confidentiality. Prior to signature, the staff member will ask the participant if they have any questions and, if not, to briefly review their understanding of their participation to be sure the information was clearly understood. The person obtaining consent will emphasize that participation is voluntary and that participants can choose to join or, if they do join, leave the study at any point without any repercussions. Study staff will frequently refer to pages, headings or some other marker in the ICF to make sure the participant is following along.

Persons agreeing to provide consent will sign the ICF as follows: a. Touch screen - persons will use finger or mouse to sign; b. No touch screen - persons will use a mouse to sign. After signing, person will submit by clicking on/touching the "Submit" button on the REDCap screen displaying the ICF. REDCap has two settings to send signed ICFs to participants and both will be employed to allow participants to have their choice of either downloading a pdf of the signed ICF or receiving an email with signed ICF attached.

For consents in person, the participant's identification is checked when coming to the consent face-to-face meeting. When a participant appears for an appointment, they will be thoroughly informed of all study procedures, potential risks, benefits, and that one can discontinue participation in the study at any time without risk to subsequent care at the place(s) where health care is received, etc.

Participants in couples must both consent to the study to be enrolled as partners. They can be consented together.

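### Aim 1 power for the companion exam: 200 couples does not fit the plan's 800 persons, and on the count that fits, 0.81 matches 78% sensitivity, not the 70% named

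*Combined protocol and SAP*

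**What the plan says.** Under STATISTICAL ANALYSIS, Aim 1, power to detect sensitivity of at least 70% "among 600 individuals is 0.90 and 0.81 among 200 couples". The same section gives a null of 50%, a one-sample test for a proportion, two-sided alpha of 0.05 and an 11% prevalence of abnormality per person. Just before the power statement it gives pilot-based sensitivities of at least 70% for the self-exam (ASE) and 78% for the ACE.

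The plan carries two ACE targets. The central hypothesis (STUDY PURPOSE, repeated under Aim 1 of the analysis section) sets at least 70% for both exams. The Aim 1 statement beginning "Hypothesis: ASE and ACE sensitivity will be" sets at least 70% for ASE and at least 78% for ACE.

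On counts, SAMPLE SIZE gives "800 participants completing Visit 1: 400 in Chicago and 400 in Houston". The Aim 2 sample-size paragraph expects 11% of persons, n=88, "to have an abnormality at Visit 1 (based on pilot data"), and subtracts dropouts and non-resolving cases from 800. On couples, Informed Consent Process says "Participants in couples must both consent to the study to be enrolled as partners", and Visit 1 Detail says "each partner will ask the other for consent before performing the ACE".

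**The concern.** The unit in the power sentence conflicts with the rest of the plan, and the sentence names one sensitivity (70%) for two exams that have different assumed values. As printed, it credits the ACE with 0.81 power at 70%.

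What is at stake is how the ACE result will be read. With about 22 abnormal persons, a true sensitivity of 70% would give a non-significant result against 50% about half the time or more. A reader who trusts 0.81 at 70% could take such a result as evidence against the companion exam, when it would say little either way.

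**Working it through.** **Head count**

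- As printed: 600 + 2 × 200 = 1,000 persons; 0.11 × 1,000 = 110 abnormal.
- Elsewhere in the plan: 800 persons; 0.11 × 800 = 88 abnormal.
- With 600 individuals kept: 800 − 600 = 200 persons, or 100 couples. Abnormal: 0.11 × 600 = 66 and 0.11 × 200 = 22; 66 + 22 = 88, which agrees.
- Cross-check from the participant time-burden table, "estimated 28 persons in each city will have discordant result": the Background reports for the pilot "There was 93% concordance between" participant and clinician, so 7% discordant. 0.07 × 400 = 28 per city, which matches; 0.07 × 500 = 35 does not.

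**Power formula**

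Power = Pr(X in the rejection region), X ~ Binomial(n, p), where n is the number abnormal. The null is 0.50 and alpha is two-sided 0.05. The z-test rejects when |X − n/2| / √(n/4) > 1.96. The exact test rejects when twice the smaller binomial tail is at most 0.05.

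- n = 22, z-test: for X = 16, 5 / √5.5 = 2.13; for X = 15, 4 / √5.5 = 1.71. Upper rejection limit 16; actual size 0.0525.
- n = 22, exact: the two-sided p-value at 16 is 0.0525, so the upper limit is 17.
- n = 66, z-test: for X = 41, 8 / √16.5 = 1.97. Upper limit 41; actual size 0.064.
- n = 66, exact: upper limit 42.

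**The plan's own figures, then the corrected ones**

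| Exam and count | True sensitivity | Exact | z-test | Plan prints |
|---|---|---|---|---|
| ASE, 66 abnormal | 70% | 0.90 | 0.93 | 0.90 |
| ACE, 22 abnormal (100 couples) | 78% | 0.65 | 0.81 | – |
| ACE, 22 abnormal (100 couples) | 70% | 0.31 | 0.49 | – |
| ACE, 44 abnormal (200 couples, literal) | 70% | 0.78 | 0.78 | 0.81 |

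The ASE figure of 0.90 reproduces with the exact test, and 0.81 reproduces with the z-test for 22 persons at 78%. Neither test gives both: the ASE/ACE pairs are 0.90/0.65 (exact) and 0.93/0.81 (z-test).

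**Chance of a non-significant ACE result with 22 abnormal**

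- True 70%: 1 − 0.49 = 0.51 (z-test); 1 − 0.31 = 0.69 (exact).
- True 78%: 1 − 0.81 = 0.19 (z-test); 1 − 0.65 = 0.35 (exact).

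For example, 15 of 22 detected (68%) is non-significant by both tests, and its Wilson 95% interval is 0.47 to 0.84, which contains 50%, 70% and 78%.

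**The case against.** The strongest reply is that this is a labelling slip and that 0.81 is correct. The plan gives 78% for ACE immediately before the power statement and again in the Aim 1 hypothesis. With 22 abnormal persons at 78%, the ordinary z-test gives 0.81. This largely stands, and it rules out a stronger reading that a reader might infer: that ACE power was miscalculated and is really 0.31 to 0.49. That reading corrects the unit but keeps 70% as the only ACE alternative, and the documents do not support setting the plan's own 78% aside. What the reply does not remove is that the sentence names 70%, that the central hypothesis sets 70% for ACE too, and that the unit is still wrong.

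A second reply takes 200 couples literally. With 44 abnormal, power at 70% is 0.78, close to 0.81, so the power arithmetic does not exclude this reading. The counts do: it needs 1,000 persons, or else 400 individuals instead of the stated 600.

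A third reply is that little changes in practice, because Aim 1 is mainly estimation and neither the planned test nor the sensitivity estimate is affected. That is true, and it is why the remedy is a change of wording.

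**Conclusion.** The power sentence is wrong as written for the ACE. Its unit implies 1,000 persons and about 110 abnormal, against 800 and 88. On the only count that fits with 600 individuals (200 persons in 100 couples, about 22 abnormal), 0.81 does not hold at the 70% named, where power is 0.31 (exact) or 0.49 (z-test). It is consistent with the plan's 78% for ACE by the z-test (0.81), but not by the exact test (0.65).

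The head count and the power at 70% are firm, given 11% prevalence, a null of 50%, two-sided 0.05 and independent results; the power statement does not mention correlation within couples. That 78% was the intended alternative is a reasonable inference only: the plan names PASS13 but not the procedure, and neither test reproduces both printed figures. The documents do not show that the ACE sample was planned on a faulty calculation or that enrolment should change.

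**What to change.** Restate the sentence as: ASE, 600 individuals, about 66 abnormal; ACE, 200 persons in 100 couples, about 22 abnormal. Name one test for both exams and give ACE power at both of the plan's targets:

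- Exact two-sided test: ASE 0.90 at 70%; ACE 0.65 at 78% and 0.31 at 70%.
- z-test: ASE 0.93 at 70%; ACE 0.81 at 78% and 0.49 at 70%. If this test is chosen, state that its actual size is 0.064 with 66 abnormal and 0.0525 with 22, both above the plan's 0.05.

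Commit to reporting ACE sensitivity with a 95% confidence interval, so that a non-significant result is not taken as evidence against the companion exam.

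The cost is one reworded sentence, one named test and one interval. The downside is that the stated ACE power becomes less favourable at 70%, and also at 78% if the exact test is chosen.

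### The 0.87 power stated for the Houston–Chicago equivalence test of ASE sensitivity is close to zero once only participants with an abnormality are counted

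*Combined protocol and SAP*

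**What the plan says.** The AIMS section (Aim 1) includes the hypothesis that ASE sensitivity does not differ between the Houston and Chicago clinics. STATISTICAL ANALYSIS, Aim 1, sets out the test: "We will then conduct a test of equivalence using two, one-sided likelihood score tests to compare ASE sensitivity in Houston vs Chicago clinics". It gives the test's purpose: "thus, we will assess the homogeneity of Houston and Chicago sensitivity before combining results". The margin is set where the plan "assumes that a difference of less than 0.15 constitutes equivalent sensitivity". The power claim is that "we have at least 0.87 power to detect a lack of equivalence in sensitivity between the cities". The plan attaches a condition to this claim, namely that it applies "if the actual observed difference ranges from 0 to 0.05".

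The sample size behind that figure is not printed. The same section gives 600 individuals doing the ASE, an expected 11% with an abnormality at Visit 1, a planning ASE sensitivity of 70%, and alpha 0.05. The SAMPLE SIZE section gives "800 participants completing Visit 1: 400 in Chicago and 400 in Houston".

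**The concern.** The denominator of sensitivity is the number of participants with an abnormal DARE, not the number enrolled. At 11% prevalence only about one ASE participant in nine contributes. A 0.15 margin on a difference of two proportions near 0.70 needs well over a hundred contributing people per city, and the design expects about 33.

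City equivalence is a named Aim 1 hypothesis, and STUDY PURPOSE lists replication of the pilot finding at a second clinic among the next steps. A reader told that power is at least 0.87 would naturally take a failed test as evidence that the cities differ, when it would be the expected result for identical cities. If combining the cities were made to depend on the test, each city would be analysed alone with about 33 abnormal cases. Power for sensitivity 0.70 against 0.50 would then fall from about 0.90 to about 0.60 (exact) or 0.64 (normal approximation).

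The sentence also describes the power the wrong way round. Two one-sided tests have power to conclude equivalence, not to find its absence. The 0 to 0.05 should be a true difference, not an observed one.

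**Working it through.** **Inputs**
- Two one-sided score tests, margin ±0.15, true difference 0 to 0.05, planning sensitivity 0.70, 600 ASE individuals, 11% abnormal (all from STATISTICAL ANALYSIS, Aim 1).
- 400 participants per city (SAMPLE SIZE).
- Assumption: the 600 individuals split equally, 300 per city. The plan does not give the ASE split by city.
- Assumption: alpha 0.05 for each one-sided test, the usual reading for this procedure.

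**Contributing participants**

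600 × 0.11 = 66 abnormal ASE participants, so 66 / 2 = 33 per city.

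**Method**

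Exact binomial enumeration of the two one-sided tests with the Farrington-Manning score statistic. As a check, the normal approximation is

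power = Φ[(0.15 − d)/SE − 1.645] + Φ[(0.15 + d)/SE − 1.645] − 1, set to 0 if negative, with SE = √[p1(1 − p1)/n + p2(1 − p2)/n].

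**Step 1: reproduce the stated figure, n = 300 per city**
- d = 0: SE = √(0.42/300) = 0.0374. 0.15/0.0374 − 1.645 = 2.36 and Φ = 0.991, so power = 2 × 0.991 − 1 = 0.982. Exact: 0.982.
- 0.70 versus 0.75: SE = √[(0.21 + 0.1875)/300] = 0.0364. 0.10/0.0364 − 1.645 = 1.10, so power is 0.865 (the second term is practically 1). Exact: 0.867.

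This matches a claim of at least 0.87 over differences of 0 to 0.05. Alpha 0.025 per side gives 0.788 at 0.70 versus 0.75 and does not match.

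**Step 2: the same test with n = 33 per city**
- SE at d = 0 is √(0.42/33) = 0.1128. The 90% confidence interval half-width is 1.645 × 0.1128 = 0.186, wider than the 0.15 margin. With both observed sensitivities near 0.70, the interval cannot fit inside ±0.15.
- Normal-approximation power: 0.15/0.1128 − 1.645 = −0.315 and Φ = 0.376. 2 × 0.376 − 1 is negative, so power is 0.
- Exact power: 0.0001 at d = 0 and 0.0005 at 0.70 versus 0.75.

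**Step 3: compare with the neighbouring power figure**

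The same paragraph gives 0.90 power for ASE sensitivity of 0.70 against 0.50 among 600 individuals. With 66 abnormal cases the exact two-sided power is 0.895; with 600 it would be 1.00. That calculation did apply the 11%, so the two figures rest on different denominators for the same quantity.

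**Step 4: vary the assumptions** (exact, alpha 0.05 per side unless stated)

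| Scenario | Power |
|---|---|
| 45 per city (15% abnormal) | 0.02 to 0.03 |
| 44 per city (all 88 abnormal persons, ASE and ACE) | 0.01 to 0.02 |
| 60 per city (20% abnormal) | 0.11 to 0.13 |
| 66 per city | 0.19 to 0.21 |
| 150 per city (50% abnormal) | 0.61 to 0.77 |
| 25 and 41, unequal split | about 0 |
| 33 per city, true sensitivity 0.80 in both | 0.014 |
| 33 per city, true sensitivity 0.90 in both | 0.20 |
| 33 per city, alpha 0.10 per side | about 0.09 |

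**Step 5: what 0.87 would need**
- d = 0: 0.42 × [(1.645 + 1.514)/0.15]² = 186.3, so about 187 abnormal ASE participants per city. 187/0.11 = 1,700 ASE participants per city.
- 0.70 versus 0.75: about 303 abnormal per city (exact 0.870). 303/0.11 = about 2,750.
- 0.70 versus 0.65: about 336 abnormal per city (exact 0.872). 336/0.11 = about 3,050.
- With 33 per city and d = 0, 80% power needs a margin of (1.645 + 1.282) × 0.1128 = 0.33.

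**The case against.** The plan does not state the sample size behind 0.87, so the use of 300 per city is an inference. The match also depends on direction: at 300 per city, 0.70 versus 0.65 gives 0.840, so the claim holds only if the second city is the better one. Both points stand, but they concern how the figure arose. Whatever produced it, about 33 abnormal participants per city cannot deliver it.

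The hypothesis is sensitivity of at least 70%, and power rises if the truth is higher. This is fair: near-zero power is tied to the planning value of 0.70. Even at 0.90 in both cities, power is only 0.20.

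The plan gives no rule that blocks pooling when equivalence is not shown, and the central hypothesis (sensitivity against 50%) is unaffected, since its 0.90 reproduces. This also stands. The loss of power in separate city analyses is therefore conditional. The error in the stated power for the city hypothesis is not.

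Finally, dropping the test is one remedy among several. Correcting the power figure follows from the arithmetic; what to do with the test afterwards is a design choice.

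**Conclusion.** The concern holds. With the plan's own 11% prevalence, 600 ASE individuals, 0.70 sensitivity and 0.15 margin, power to conclude city equivalence is 0.0001 to 0.0005, against a stated minimum of 0.87. This assumes an equal split of ASE individuals between cities and alpha 0.05 per side. An unequal split or alpha 0.025 per side leaves it at about zero. None of the variations tried reaches 0.87, including a prevalence of 50%. The most likely cause is that all 300 ASE participants per city were entered as the sensitivity denominator. The city-equivalence part of Aim 1 cannot realistically be supported as designed, and a failed test would say almost nothing about whether the cities differ.

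**What to change.** 1. Replace the power statement. Say that with about 33 DARE-abnormal ASE participants per city, sensitivity 0.70 and margin 0.15, power to conclude equivalence is below 0.001 for true differences of 0 to 0.05. State the denominator and the alpha per side.
2. Correct the wording so that the power is to conclude equivalence and the difference is the true one.
3. Remove the equivalence test as the step before combining cities, and remove the claim that equivalence can be shown. Estimate pooled ASE sensitivity stratified by, or adjusted for, city. Report the city difference with its 95% confidence interval as descriptive; the expected half-width is 1.96 × 0.1128 = 0.22.
4. If the sponsor prefers to keep the test, label it as having almost no power, or justify a wider margin (about 0.33 for 80% power). In either case, state a pooling rule that does not depend on it, and say that failure to show equivalence is not evidence of a difference.

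The cost is protocol and SAP wording and a less favourable stated figure. No extra participants or data are needed.
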